Appendix 9 HAQ-DI[©] Questionnaire

HEALTH ASSESSMENT QUESTIONNAIRE (HAQ-DI)[©]

Name: _____ Date: _____

Please place an "x" in the box which best describes your abilities OVER THE PAST WEEK:

	WITHOUT ANY DIFFICULTY	WITH SOME DIFFICULTY	WITH MUCH DIFFICULTY	UNABLE TO DO
DRESSING & GROOMING				
Are you able to:				
Dress yourself, including shoelaces and buttons?				
Shampoo your hair?				
ARISING				
Are you able to:				
Stand up from a straight chair?				
Get in and out of bed?				
EATING				
Are you able to:				
Cut your own meat?				
Lift a full cup or glass to your mouth?				
Open a new milk carton?				
WALKING				
Are you able to:				
Walk outdoors on flat ground?				
Climb up five steps?				

Please check any AIDS OR DEVICES that you usually use for any of the above activities:

 Devices used for Dressing (button hook, zipper pull, etc.)	 Built up or special utensils	 Crutches
	 Cane	 Wheelchair
 Special or built up chair	 Walker	

Please check any categories for which you usually need HELP FROM ANOTHER PERSON:

 Dressing and grooming	 Arising	 Eating	 Walking
--	----------------------------------	---------------------------------	----------------------------------

Please place an "x" in the box which best describes your abilities OVER THE PAST WEEK:

	WITHOUT ANY DIFFICULTY	WITH SOME DIFFICULTY	WITH MUCH DIFFICULTY	UNABLE TO DO
HYGIENE				
Are you able to:				
Wash and dry your body?				
Take a tub bath?				
Get on and off the toilet?				
REACH				
Are you able to:				
Reach and get down a 5 pound object (such as a bag of sugar) from above your head?				
Bend down to pick up clothing from the floor?				
GRIP				
Are you able to:				
Open car doors?				
Open previously opened jars?				
Turn faucets on and off?				
ACTIVITIES				
Are you able to:				
Run errands and shop?				
Get in and out of a car?				
Do chores such as vacuuming or yard work?				

Please check any AIDS OR DEVICES that you usually use for any of the above activities:

 Raised toilet seat	 Bathtub bar	 Long-handled appliances for reach
 Bathtub seat	 Long-handled appliances in bathroom	 Jar opener (for jars previously opened)

Please check any categories for which you usually need HELP FROM ANOTHER PERSON:

 Hygiene	 Reach	 Gripping and opening things	 Errands and chores
----------------------------------	--------------------------------	--	---

Your ACTIVITIES: To what extent are you able to carry out your everyday physical activities such as walking, climbing stairs, carrying groceries, or moving a chair?

COMPLETELY MOSTLY MODERATELY A LITTLE NOT AT ALL

Your PAIN: How much pain have you had IN THE PAST WEEK?

On a scale of 0 to 100 (where zero represents "no pain" and 100 represents "severe pain"), please record the number below.

--	--	--

Your HEALTH: Please rate how well you are doing on a scale of 0 to 100 (0 represents "very well" and 100 represents "very poor" health), please record the number below.

--	--	--

Courtesy of https://integrationacademy.ahrq.gov/center/default/files/-DI_0.pdf

Statistical Analysis Plan (SAP)

**Evaluation of the Precision and Sensitivity of
Tilmanocept Uptake Value (TUV) on Tc 99m
Tilmanocept Planar Imaging**

[figure not shown]
Study No: NAV3-31

Version 1.1

July 6, 2021

**Prepared for
Navidea Biopharmaceuticals, Inc.
[name]
[name]**

**Prepared by
STATKING Clinical Services
[name]
[name]
[contact]
www.statkingclinical.com**

STATKING Clinical Services

Approval Page

By entering into this Statistical Analysis Plan (SAP), the parties acknowledge and agree that this SAP shall be incorporated into and subject to the terms of the Master Services Agreement (MSA). Any changes requested by Client to this SAP shall be subject to Section I.C of the MSA requiring a mutually agreed upon "Change Order" prior to any modification of the procedures set forth herein.

I agree to the format and content of this document.

[figure not shown]
Approved by:

[name]
Chief Medical Officer
Navidea Biopharmaceuticals
[name]
[name]
[contact]

Date

[figure not shown]

[name], MS, CCRA
Senior Director, Clinical Research & Operations
Navidea Biopharmaceuticals
[name]
[name]
[contact]

Date

Authored by:

[name]
Director of Biostatistics
STATKING Clinical Services
[name]
[name]
[contact] [name]
[contact]

Date

Approved by (internal review):

[name]

[name], MS

Statistician

STATKING Clinical Services
[name]
[name]
[contact] [name]
[contact]

07/07/2021

Date

Approved by:

[name]

[name]
Project Manager
STATKING Clinical Services
[name]
[name]
[contact] [name]
[contact]

7-7-2021

Date

Revision History

Version 1.0 to 1.1:

- Updated the TUV prediction algorithms 1 and 4 in Section 4.2.2 to include a 10% decrease as a predicted responder. The prior SAP version defined a responder as one with a strictly greater than 10% decrease.
- Added clarification in Section 4.2.2 that the TUV prediction algorithms are to be implemented after rounding the change in TUV calculations to the nearest integer percentage (i.e., nearest hundredths place for a proportion).

List of Abbreviations and Definitions of Terms

Term	Definition
Δ	Greek letter delta, used to represent the change in a particular variable
μg	microgram
ACPA	anti-citrullinated protein/peptide antibody

6.0 OTHER RELEVANT DATA ANALYSES/SUMMARIES	29
6.1 Patient Completion	29
6.3 Study Drug Administration.....	29
6.4 RA Evaluation and Screening Physical Exam.....	29
6.5 Concomitant Medications.....	29
7.0 LIST OF ANALYSIS TABLES, FIGURES AND LISTINGS	31
9.0 REFERENCES.....	35
APPENDIX A – TABLES, FIGURES AND LISTING SPECIFICATIONS	36
APPENDIX B – TABLE SHELLS	38

INTRODUCTION

Description

This Statistical Analysis Plan (SAP) is consistent with Amendment 4 of the study protocol (dated 2 February 2021) and includes the latest details of efficacy and safety summaries to be included in the clinical study report (CSR).

The preparation of this SAP was done in accordance with STATKING Clinical Services SOP SCI 02-54, Statistical Analysis Plans.

1.0 Synopsis of Study Design/Procedures

This study is a prospective, open-label, multicenter, evaluation of the reliability and sensitivity of Tilmanocept Uptake Value (TUV) assessments based on planar imaging localization of intravenously (IV) injected Tc 99m tilmanocept to skeletal joints in subjects with and without active rheumatoid arthritis (RA).

The study has three arms. Arm 1 consists of Healthy Control (HC) subjects. Arm 2 consists of RA patients on stable therapy. Arm 3 consists of RA patients who are candidates for initiation of, or change to a new anti-tumor necrosis factor α (TNF α) biological disease-modifying antirheumatic drug (bDMARD) treatment.

The objectives of the study are:

Primary Objectives:

- To assess the longitudinal precision of TUV_{joint} and TUV_{global} on planar imaging in subjects with clinically diagnosed active RA on stable anti-rheumatic therapy.
- To evaluate camera-specific precision of TUV_{joint} and TUV_{global} on planar imaging in HCs and in subjects with clinically diagnosed active RA using centralized and standardized imaging parameters.
- To assess the correlation of TUV and changes in TUV with changes in clinical assessments at multiple time points after initiation of a new anti-anti-TNF α bDMARD therapy.

Secondary Objectives:

- To assess the temporal post-injection stability of TUV_{joint} and TUV_{global} at a dose of 150mcg tilmanocept radiolabeled with 10 mCi of Tc 99m.
- To establish normal ranges for TUV_{joint} in HCs.

- To assess Tc 99m tilmanocept anatomic localization based on single photon emission computed tomography/ computed tomography (SPECT/CT) imaging of the synovial space in hands and wrists.

Safety Objective:

- To evaluate safety through the examination of adverse event (AE) incidence and changes over time in laboratory tests, vital signs, and physical examination findings.

1.1 Design and Treatment

Subjects will receive the administration of Tc 99m tilmanocept through an IV route of administration. All subjects will receive a 150 µg mass dose of tilmanocept labeled with 10 mCi of Tc 99m in a 3 ml volume. Following injection a 10 ml sterile normal saline flush will be administered. The preferred site of IV placement will be between the elbow and wrist.

Arm 1 HC subjects receive a single administration of 10 mCi of Tc 99m in a 150 µg mass dose of tilmanocept. Arm 2 RA subjects receive two (2) IV administrations of 10 mCi Tc 99m in a 150 µg mass dose of tilmanocept. Arm 3 RA subjects receive up to four (4) administrations of 10 mCi Tc 99m in a 150 µg mass dose of tilmanocept.

Table 1 Study arms

Arm	Subjects	Evaluations
1	HC subjects clinically free of any inflammatory disease and/or joint pain.	Image, Re-image
2	Subjects with clinically diagnosed RA who have been on stable anti-rheumatic therapy.	Image, Re-image Test, Re-test
3	Subjects with clinically diagnosed RA who are candidates for initiation of, or change to, a new anti-TNF α bDMARD treatment.	Positive Predictive Value, Negative Predictive Value, Clinical Concordance

1.2 Study Procedures

Subjects will visit the study site for screening procedures up to 30 days (Day -30 to Day -1) before enrollment into the study. Screening procedures (demographics, vital signs, medical history, blood and urine samples for clinical

labs, RA specific labs, urine pregnancy testing for subjects of childbearing potential, and physical exam) will be completed along with RA evaluations using the 2010 ACR/EULAR score. The DAS28 score instrument will be used in Arms 2 and 3.

Subjects arriving for Study Day 0 will be considered enrolled in the study. On Day 0 subjects will receive Tc 99m injection and imaging procedures. Pre-injection procedures include the following: a urine pregnancy test will be administered to all subjects with childbearing potential. Up to 30 minutes prior to drug administration an ECG will be performed, followed by assessment of vital signs and AEs. After pre-injection procedures are completed subjects will receive a single IV dose with 150 μ g of tilmanocept radiolabeled with 10 mCi of Tc 99m. Within 30 minutes of injection, subjects will receive an ECG followed by vital sign and AE check. Whole body planar imaging will be conducted on the subject at the time points specified for the arm into which he/she was enrolled (see Section 1.0). For subjects in Arms 1 and 2, planar images of the whole body and bilateral hands and wrists will be taken at 60 (\pm 15) minutes and at 180 (\pm 15) minutes after injection. Blood will be drawn for clinical laboratory evaluations after all image acquisitions have been completed.

On Study Day 5 (\pm 3 days) a safety follow-up telephone call will include a review of concomitant medications and assessment of adverse events. Arm 1 HC subjects have completed the study at this point.

On Study Day 8 (\pm 1 day) RA subjects in Arm 2 will receive repeat Tc 99m tilmanocept imaging. Pre-injection procedures include the following: a urine pregnancy test will be administered to all subjects with childbearing potential. Up to 30 minutes prior to drug administration an ECG will be performed, followed by assessment of vital signs and AEs. After pre-injection procedures are completed subjects will receive a single IV dose with 150 μ g of tilmanocept radiolabeled with 10 mCi of Tc 99m. Within 30 minutes of injection, subjects will receive an ECG followed by vital signs and AE assessment. Planar images of the whole body and bilateral hands and wrists will be taken at 60 (\pm 15) minutes and 180 (\pm 15) minutes after injection. Following the 180 minute planar imaging, subjects will have SPECT/CT images of the bilateral hands and wrists taken. Blood will be drawn for clinical laboratory evaluations after all image acquisitions have been completed.

From 1 to 3 days of the second imaging day (i.e., Study Day 9 to 11 if imaging is done on Study Day 8), a safety follow-up telephone call will be made to review concomitant medications and AE check. Arm 2 RA subjects have completed the study at this point.

For RA subjects in Arm 3, Study Day 0 is modified to include planar whole body and planar images of the hands and wrists once only at 60 minutes post-injection. All other procedures remain the same on Study Day 0. The new therapy (anti-

TNF α bDMARD) will be initiated following the Day 0 imaging. A safety follow-up telephone call will be conducted on Study Day 5 (\pm 3 days). Follow-up images of the hands and wrists and whole body will be made at 5 weeks (\pm 1 week) after initiation of the new anti-TNF α bDMARD therapy using the same procedures as in Arm 2 Day 8, except that no images will be taken at 180 minutes in Arm 3 and the post imaging clinical laboratory assessments will include an RA panel. CDAI, DAS28, HAQ-DI, WPI, and an AE check will also occur at this visit. A safety follow-up telephone call will be conducted 1 to 3 days later. At weeks 12 (\pm 1 week) and 24 (\pm 1 week) after initiation of the new anti-TNF α bDMARD therapy, Arm 3 subjects will have a return visit for imaging and assessment of their RA status. These visits will include clinical laboratory assessments and RA-specific labs (post imaging), tilmanocept injection and image acquisition 60 (\pm 15) minutes following injection, CDAI, DAS28, HAQ-DI, WPI, and AE check at both of these time points. ACR Response Criteria will be assessed at weeks 5, 12 and 24. After the week 24 visit, Arm 3 RA subjects have completed the study.

The centralized core image laboratory contracted by Navidea Biopharmaceuticals completed a quantitative read of the images to determine the amount of radiotracer uptake in the joints (TUV_{joint}) and in the brain (TUV_{brain}) for Interim Analysis 2. The core image laboratory will also evaluate localization of Tc 99m tilmanocept in the 180 minute planar and SPECT/CT images of Arm 2 RA patients. Navidea internal work instructions and imaging charter will be followed for all other quantitative and qualitative reads for all other imaging data.

1.3 Sample Size

Up to 105 subjects from up to 10 study centers will be enrolled into Arms 1, 2, and 3 as allocated below, and imaged. Arm 1 will have N = 38 evaluable subjects, Arm 2 will have N = 38 evaluable subjects, and Arm 3 will have N = 29 evaluable subjects. A subject is considered evaluable if he/she meets the criteria for the analysis population and has the data necessary for computing the primary endpoint.

The sample size for Arm 1 was determined to assess temporal stability of the 150 μ g mass dose/10mCi radiolabeling dose. The sample size for Arm 2 was determined to power a hypothesis test at 0.80:

$$\begin{aligned} H_0: \pi &\leq 0.80 \\ &\text{vs} \\ H_a: \pi &> 0.80, \end{aligned}$$

where π represent the fraction of unsigned differences less than 7.5% The sample size for Arm 3 was determined to provide a lower 97.5% confidence limit for the rank correlation of at most 0.15 when $\rho = 0.70$, using Fisher's Z-transformation methods.

2.0 Data Analysis Considerations

2.1 Types of Analyses

Data analyses described in this SAP will consist of analyzing efficacy and safety data.

2.2 Analysis Populations

The following analysis populations will be used in the study:

Safety Population – The safety population includes all patients that have been enrolled in the study and injected with at least one dose of Tc 99m tilmanocept.

Intent-to-Diagnose (ITD) Population – The ITD population includes all patients that have been enrolled in the study, injected with Tc 99m tilmanocept, and received all imaging and evaluations necessary for the primary endpoint(s) appropriate to their respective arm.

Per Protocol (PP) Population: The PP population will include all ITD subjects without major protocol violations. All protocol deviations will be classified as major or minor prior to database lock.

All efficacy analyses will be carried out on the ITD and PP populations with the ITD population being the primary analysis set. All analyses of safety data and baseline subject characteristics will be carried out on the safety population. A data listing displaying the patients excluded from each population will be created, as shown in Appendix B.

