9.5.5 Handling of Missing Values

The analysis of the efficacy variables will be carried out on the observed data, i.e. a complete case analysis.

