2.3 Missing Data Conventions

No missing value imputation will be used in this analysis. All analyses will be based on the observed data.

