The Kendall rank correlation between $\Delta TUV_{global[5w]}$ with $\Delta CDAL_{12w}$ and $\Delta CDAL_{24w}$ will be computed and a 95% confidence interval for its value will be computed using Fisher's Z-transformation. Similarly, the Kendall rank correlation between $\Delta TUV_{global[5w]}$ with changes from baseline in DAS28 and in each of the ACR Response Criteria components at weeks 12 and 24 will be computed and a 95% confidence interval for its value will be computed using Fisher's Z-transformation. The marginal distributions of the variables will be characterized with the mean, standard deviation, and the number of data pairs.

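### An Arm 3 subject who leaves between Week 12 and Week 24 is also removed from the Week 12 analyses, because ITD requires every primary-endpoint assessment for the arm

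*SAP*

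**What the plan says.** Both documents give the same entry rule for ITD: enrolled, injected, and "received all imaging and evaluations necessary for the primary endpoint(s) appropriate to their respective arm" (SAP 2.2; protocol 9.5.1).

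For Arm 3, SAP 4.1.1 and 4.2.1 pair the Week 5 change in global TUV with the change in CDAI at Weeks 12 and 24. They do the same for the other clinical measures: "changes from baseline in DAS28 and in each of the ACR Response Criteria components at weeks 12 and 24 will be computed". Protocol 9.3 also names both weeks, for CDAI and ACR response.

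On analysis sets, SAP 2.2 states: "All efficacy analyses will be carried out on the ITD and PP populations with the ITD population being the primary analysis set". It adds: "The PP population will include all ITD subjects without major protocol violations".

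On missing data, SAP 2.3 reads: "No missing value imputation will be used in this analysis. All analyses will be based on the observed data". Protocol 9.5.5 says the efficacy analysis is "carried out on the observed data, i.e. a complete case analysis". Neither document defines an efficacy set by endpoint or time point, and neither plans a sensitivity analysis for dropout.

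Protocol 7.1.3 asks for an attempt at a final imaging visit and all clinical assessments when an Arm 3 subject leaves between Weeks 16 and 24.

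**The concern.** The name suggests a broad set, but in Arm 3 ITD is a set of Week 24 completers. Whether a subject's Week 12 data are used depends on something that happens after Week 12. That wastes usable data in an arm planned at 29 subjects. It also selects on a later event that may well be related to outcome: a subject whose new therapy is not working has a reason to leave. Protocol 1.1 itself notes that a significant portion of RA patients do not respond to therapy.

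At stake are the Week 12 rank correlations (primary) and the tables that set a predictor against the Week 12 clinical outcome (secondary: Tables 44, 45, 48, 49, 52, 53, 62 and 63). The shell for Table 44 tests PPV and NPV against 0.6, so a shift caused by selection alone could affect a formal test.

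**Working it through.** **Step 1. The chain of rules.**
- Weeks 12 and 24 are both primary in Arm 3 (SAP 4.2.1).
- ITD needs all primary evaluations for the arm (SAP 2.2), hence Week 24.
- Every efficacy table uses ITD or PP, and PP lies inside ITD.
- So a subject with baseline, Week 5 and Week 12 data but no Week 24 data is in neither set and in no Week 12 efficacy table.

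**Step 2. The plan's own figure.** SAP 1.3 says "Arm 3 will have N = 29 evaluable subjects", based on Fisher's Z at a rank correlation of 0.70 and a figure of 0.15. With standard error 1/sqrt(n-3):
- atanh(0.70) = 0.867 and 1.96/sqrt(26) = 0.384.
- The limits are tanh(0.483) = 0.449 and tanh(1.252) = 0.849.

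The lower limit is not 0.15, and the distance to it is 0.251. The distance to the upper limit is 0.149, and 29 is the smallest n that keeps this at or below 0.15. As worded, 29 is not reproduced. The present point does not depend on it.

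**Step 3. Loss of precision.** The documents state no dropout rate, so 5% to 30% is assumed, starting from 29 subjects with Week 12 data. The SAP gives no variance formula. Two forms are shown: the Pearson form 1/(n-3) at r = 0.70, and a common Kendall form 0.437/(n-4) at tau = 0.494 (about what r = 0.70 implies under normality).

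| Loss before Week 24 | Week 12 n under the ITD rule | 95% CI, Pearson form | 95% CI, Kendall form |
|---|---|---|---|
| 0% | 29 | 0.449 to 0.849 | 0.274 to 0.664 |
| 5% | 28 | 0.442 to 0.851 | 0.270 to 0.667 |
| 10% | 26 | 0.429 to 0.855 | 0.259 to 0.673 |
| 20% | 23 | 0.405 to 0.863 | 0.239 to 0.685 |
| 30% | 20 | 0.373 to 0.872 | 0.214 to 0.699 |

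If Week 12 analyses did not require Week 24, the first row would apply whatever happened after Week 12. To keep 29 complete subjects under the present rule, 31, 33, 37 or 42 would have to be enrolled at 5, 10, 20 or 30% loss.

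**Step 4. Direction of bias, by arithmetic.** Let a fraction q of non-responders leave after Week 12 and no responders leave.
- PPV becomes PPV/(PPV + (1-PPV)(1-q)).
- NPV becomes NPV(1-q)/(NPV(1-q) + (1-NPV)).

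Starting both at 0.60, the value tested in the Table 44 shell:
- q = 0.2: PPV = 0.60/0.92 = 0.652; NPV = 0.48/0.88 = 0.545.
- q = 0.4: PPV = 0.60/0.84 = 0.714; NPV = 0.36/0.76 = 0.474.

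**Step 5. Direction of bias, by simulation.** The model is bivariate normal with correlation 0.70, 60% Week 12 responders, 60% predicted improved and 400,000 simulated subjects. All of these are assumptions.

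| Loss between Weeks 12 and 24 | tau | PPV | NPV |
|---|---|---|---|
| None | 0.49 | 0.80 | 0.69 |
| 20%, unrelated to response | 0.49 | 0.80 | 0.69 |
| 10%, non-responders only | 0.48 | 0.84 | 0.63 |
| 20%, non-responders only | 0.46 | 0.89 | 0.53 |
| 20%, the worst responses | 0.41 | 0.85 | 0.48 |

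The formulas in Step 4 agree. A 20% loss taken only from the 40% who are non-responders is q = 0.5. Then PPV = 0.796/(0.796 + 0.204 x 0.5) = 0.886 and NPV = 0.347/(0.347 + 0.306) = 0.531.

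**The case against.** The strongest reply is that an available-case analysis was intended. SAP 2.3 speaks of observed data, SAP 4.2.1 reports the number of data pairs, and the shells for Tables 19 and 21 print an n for each time point, which would be largely redundant if every Week 12 and Week 24 row used the same completers. That may well be the intention. But the missing-data convention works within the analysis set, and the set is fixed first by a rule that requires Week 24. Nothing in the text relaxes the rule by time point. If available-case analysis was meant, the wording needs correcting anyway, because two programmers could produce different denominators.

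Second, the protocol tries to secure a final visit. This stands as mitigation. It is only an attempt, it does not cover exits between Weeks 12 and 16, and no rule says whether such a visit counts as Week 24.

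Third, 29 is a count of evaluable subjects, so falling below it means missing the target. This is fair, and Step 3 is an illustration only. However, SAP 1.3 caps enrolment at 105, which equals 38 + 38 + 29 and leaves no margin, and protocol 4.5 does not replace a subject who has been injected and imaged.

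Fourth, losses would be visible: exclusions from ITD are listed and withdrawal reasons are tabulated. That is true, but listing a loss does not put the data back.

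A reader might also infer more than the documents support:
- *That the rule inflates predictive performance in general.* Only PPV rises. NPV and the rank correlation, which is the primary statistic, fall.
- *That the rule discards Arm 2 consecutive-scan pairs because Day 8 is missing.* SAP 4.2.1 says those camera-precision analyses were completed in IA-3, under an interim plan that is not among these documents. The rule now reaches only remaining Day 0 summaries such as Tables 5 and 13.
- *That missing data are left unaddressed.* Both documents state a convention. What is absent is a sensitivity analysis.

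**Conclusion.** The point holds on the literal text: the Week 12 analyses in Arm 3 are restricted to Week 24 completers, and neither efficacy set avoids this. The certain consequence is that valid Week 12 data are discarded whenever a subject leaves after Week 12 without Week 24 data. Bias is conditional. There is none if leaving is unrelated to response. If non-responders leave more often, PPV tends to rise while NPV and tau tend to fall. For an assumed loss of 10 to 20% made up only of non-responders, PPV moves from 0.80 to 0.84-0.89, NPV from 0.69 to 0.63-0.53, and tau from 0.49 to 0.48-0.46. These sizes rest on assumed loss rates, an assumed 60% responder rate and a normal model. The documents supply none of these, so the direction is more reliable than the figures. This should be corrected because the remedy is cheap. It does not show that the Week 12 results will be biased.

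**What to change.** In SAP 2.2, with matching text in protocol 9.5.1, define ITD per endpoint and time point: injected subjects with the imaging and clinical data needed for the analysis in question. State that Week 12 analyses do not require Week 24 data and that Day 0 summaries do not require Day 8. Add one sentence saying whether an early-exit visit counts as Week 24 in the analysis. Settle this before database lock.

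Optionally, add a sensitivity bound for the Week 5 TUV concordance tables (44 to 55), in which subjects with a Week 5 TUV but no later clinical assessment count as not improved. Label it a bound, because it lowers PPV and raises NPV by construction. It cannot be carried over unchanged to Tables 56 to 61, which need a Week 12 TUV.

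The cost is a few sentences in each document and, if the bound is adopted, one extra run. No new data are needed. Denominators will differ between tables, which the shells already accommodate by reporting n.
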